## 2.3 Missing Data Conventions

Date variables with missing items will be imputed as shown in Text Table 2 below.

**Table 2. Imputation rules for missing dates.**

Data	Handling Convention
Adverse event onset date	If onset date is completely missing, impute with the date of first dose.  If year is missing, impute with the year of enrollment.  If only year or if year and day are present: 
 
• If year = year of first dose, then set month and day to the date of the first dose.
 
• If year < year of first dose, then set month and day to December 31.
 
• If year > year of first dose, then set month and day to January 1.
 
 If month and year are present, but day is missing: 
 
• If year = year of first dose and
 
◦ If month = month of first dose, then set day to day of first dose.
 
◦ If month < month of first dose, then set day to the last day of the month.
 
◦ If month > month of first dose, then set day to the first day of the month.
 

 
• If year < year of first dose, then set day to the last day of the month.
 
• If year > year of first dose, then set day to the first day of the month.
 
• For all other cases, set onset date to the date of first dose.
 

Adverse event end date	If the end date is partially or completely missing, set to the last date the subject was known to be in the study.
Concomitant medications start date	If start date is completely missing, it will not be imputed.  If only year or if year and day are present, set the month and day to January 1.  If year and month are present and day is missing, set day to the first day of the month.
Concomitant medications end date	If end date is missing, frequency is "1X" and the medication is not listed as "ONGOING", then end date should be set to equal the start date.  If end date is completely missing, it will not be imputed.  If only year or if year and day are present, set the month and day to December 31.  If year and month are present and day is missing, set day to the last day of the month.

While every effort will be made to compile the data in accordance with intent-to-treat, it is likely that some subjects will have missing endpoints. Sensitivity analyses will be performed to assess the influence missing primary endpoints may have on the study's conclusions. The first analysis will be a best-case analysis, assigning infected status to all missing COVID-19 disease and VRI status in the placebo arm and non-infected status to these variables in the NTZ arm. The second sensitivity analysis will be a worst-case

analysis. This analysis will assign infected status for COVID-19 disease and VRI to missing values in the NTZ arm and non-infected status to the missing values in the placebo arm. Finally, a tipping point analysis will use multiple imputation methods to determine the allocation of infected and non-infected status to missing values in the NTZ arm which changes the study conclusions.

## 2.4 Interim Analyses

A first review for safety will be conducted by the Independent Data Monitoring Committee (IDMC) when 20% of the planned number of subjects have completed three weeks of treatment. This review will examine the available data for safety signals contained in the AE, vital sign, and clinical laboratory data.

An unblinded analysis may be performed under circumstances defined in the IDMC charter, which relate to the rate of COVID-19 illnesses and the rate of occurrence of diarrhea as an adverse event.

If conditions required for unblinding are satisfied, futility will be assessed using a conditional power approach assessing the efficacy of NTZ for the COVID-19 endpoint. The IDMC will recommend stopping for futility if the conditional power of the study at that stage is less than 30%. The conditional power will be calculated according to Chow and Chang (2007):

$$\text{Conditional Power} = 1 - \Phi \left( \sqrt{z_{1-\alpha_2}^2 - z_{1-p_1}^2} - \frac{\delta}{\sigma} \sqrt{n_2} \right).$$

In the above,  $z_{\alpha}$  refers to the  $\alpha$ -th quantile of the Standard Normal distribution,  $\alpha_2$  is the planned final significance level of the study,  $p_1 > \alpha_2$  is the  $p$ -value at the first interim analysis,  $\delta$  is the observed study effect size (i.e., the difference in observed rates in the two groups),  $\sigma$  is the observed standard error of the difference in rates at the interim, and  $n_2$  is the number of subjects remaining to be enrolled in the study.

A second review for safety and futility will be conducted by the IDMC when 50% of the planned number of subjects have completed 6 weeks of treatment. An unblinded analysis will be conducted under circumstances defined in the IDMC charter, which relate to the rate of COVID-19 illnesses, the rate of occurrence of diarrhea as an adverse event and other safety considerations. Futility will be concluded if the CMH test statistic for comparing the treatment groups on the COVID-19 endpoint is less than 0.179 (i.e., a  $p$ -value greater than 0.3278). This bound was set using O'Brien-Fleming bounds for futility with overall  $\alpha = 0.049$ .

An interim analysis of effectiveness will be performed when there are at least 25 laboratory-confirmed COVID-19 cases observed among the study participants. If the assumptions made in the power calculations are correct (COVID-19 rate is 0.05 in the placebo group and 0.01 in the NTZ group) we expect to observe only 24 events during the entire study. If this milestone is reached early, it indicates that the assumptions were

conservative and merit review given the high rate of mortality observed from COVID-19 illness in this population. This review will be conducted by the IDMC in accordance with its charter and will encompass both a safety and efficacy determination. In the event that the timing of the interim analysis of effectiveness is near that of the second review for safety and futility, analyses of safety, futility and effectiveness may be performed simultaneously.

O'Brien-Fleming bounds are used to set the Type I error rates for the third interim and final analyses. The interim efficacy review will be performed with  $\alpha = 0.0052$  (overall), allocated 0.005 to the COVID-19 endpoint and 0.0002 to the VRI endpoint. The final data analysis (if the efficacy hypotheses are not rejected at the interim review) will be performed with  $\alpha = 0.048$ , allocated 0.047 to the COVID-19 endpoint and 0.001 to the VRI endpoint. Power at the interim analysis is 31% for the COVID-19 endpoint. If the interim review for efficacy does not occur (i.e., the event count of 25 is not reached or reached too late in the study for the interim review to be useful), the alpha levels for the final analysis will be 0.049 for the COVID-19 endpoint and 0.001 for the VRI endpoint.

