8. STATISTICAL CONSIDERATIONS

8.1. Sample Size Calculations

Recent reports of COVID-19 in long-term care facilities in the United States have suggested a high rate of transmission of the SARS-CoV-2 virus, but infection control procedures may significantly decrease transmission (McMichael et al. 2020, Kimball et al. 2020). A recent study of 264 elderly volunteers (≥ 65 years of age) reported 1.6 respiratory tract infections (not laboratory-confirmed) per person-year indicating approximately a 20% probability of respiratory tract infection over a given 6-week period (Mannick et. al, 2018). Infection control procedures in place during the period covered by this clinical trial are also expected to reduce the transmission of other respiratory viruses.

For purposes of calculating our sample size, we assume that the proportion of subjects experiencing COVID-19 over a 6-week period is 5%, the proportion of subjects experiencing any VRI is 10%, and that effective prophylaxis will reduce the rate of COVID-19 and other VRIs by 80%. Influenza prophylaxis studies of oseltamivir have resulted in approximately 80% reduction of influenza illness among residents of long-term care facilities (see Tamiflu® prescribing information).

A Cochran-Mantel-Haenszel (CMH) chi-square test stratifying by 20 LTCFs will have 92.8% statistical power to detect the difference between 5% and 1% rates of occurrence of COVID-19 over all strata at an alpha of 0.049 with a total sample size of 800, allocated equally to strata (LTCFs) and treatment groups within strata. The statistical power remains >92% when the number of LTCFs is 5, 10, 16 or 20. The CMH chi-square test has 93.9% power to detect the difference between 10% and 2% rates of occurrence of VRIs over all strata at an alpha of 0.001 with 800 subjects allocated equally to 20 LTCFs. Adjusting the stratum size to assume unequal allocation while holding the effect size and total sample size constant results in negligible changes (i.e., changes in the third significant figure) in the study power.

A sample size of 800 subjects (400 per treatment group) was selected.

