### 1.3 Sample Size

Recent reports of COVID-19 in long-term care facilities in the United States have suggested a high rate of transmission of the SARS-CoV-2 virus, but infection control procedures may significantly decrease transmission (McMichael et al. 2020, Kimball et al. 2020). A recent study of 264 elderly volunteers ( $\geq 65$  years of age) reported 1.6 respiratory tract infections (not laboratory-confirmed) per person-year indicating approximately a 20% probability of respiratory tract infection over a given 6-week period (Mannick et. al, 2018). Infection control procedures in place during the period covered by this clinical trial are also expected to reduce the transmission of other respiratory viruses.

For purposes of calculating sample size, we assume that the proportion of subjects experiencing COVID-19 over a 6-week period is 5%, the proportion of subjects experiencing any VRI is 10%, and that effective prophylaxis will reduce the rate of COVID-19 and other VRIs by 80%.

A Cochran-Mantel-Haenszel (CMH) chi-square test stratifying by 20 LTCFs will have 87.1% statistical power to detect the difference between 5% and 1% rates of occurrence of COVID-19 across all strata at a two-sided alpha of 0.047 with a total sample size of 800, allocated equally to strata (LTCFs) and treatment groups within strata. The statistical

power remains >87% when the number of LTCFs is 5, 10, 16 or 20. The CMH chi-square test has 91% power to detect the difference between 10% and 2% rates of occurrence of VRIs over all strata at a two-sided alpha of 0.001 with 800 subjects allocated equally to 20 LTCFs. Both tests are insensitive to stratum size. Varying the number of subjects per stratum (LTCF) between a minimum of 8 to a maximum of 80 while holding both the effect size and total sample constant results in changes in the third significant figure of the test's power.

A sample size of 800 subjects (400 per treatment group) was selected.

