## 4.2 Efficacy Analysis

### 4.2.1 Primary Efficacy Variables

The study has two primary efficacy endpoints: reduction in symptomatic COVID-19 disease and reduction in all VRI. The study-wise  $\alpha$  level is set at 0.05, allocated with 0.049 to the COVID-19 endpoint and 0.001 to the all VRI endpoint. See Section 2.4 for details on how the study- wise  $\alpha$  level will be allocated to the interim and final analyses. For each endpoint, the following hypotheses will be tested

$$H_0: p_1 = p_2$$

$$H_1: p_1 \neq p_2,$$

here,  $p_1$  represents the probability of symptomatic disease (either COVID-19 or VRI) in the NTZ treatment group and  $p_2$  represents the probability of symptomatic disease in the placebo group.

The proportion of subjects experiencing symptomatic COVID-19 disease in the NTZ treatment group will be compared to the similar proportion in the placebo group using a two-sided CMH test with continuity correction at  $\alpha=0.047$ . The test will be stratified by LTCF. The contingency tables will be provided with rates relative to the treatment margins. A 95% confidence interval for the odds ratio of symptomatic COVID-19 infection in the NTZ group relative to the placebo group will be provided. The risk difference for the treatment groups and a 95% confidence interval for the difference will be provided.

The proportion of subjects experiencing symptomatic VRI infections in the NTZ treatment group will be compared to the similar proportion in the placebo group using a two-sided CMH test, stratified by LTCF with continuity correction at  $\alpha=0.001$ . The contingency tables will be provided with rates relative to the treatment margins. A 95% confidence interval for the odds ratio of symptomatic VRI in the NTZ group relative to the placebo group will be provided. The risk difference for the treatment groups and a 95% confidence interval for the difference will be provided.

CMH analyses of symptomatic COVID-19 disease and symptomatic VRI will be repeated with subjects divided by sex (female or male), age (65- to 79 years or 80 years and over), and race (white or non-white). Estimates and confidence intervals for the odds ratio and relative risk differences will be provided.

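### Both futility criteria in SAP 2.4 use COVID-19 alone, so if the charter allows unblinding, a trial that would succeed on VRI, its second primary endpoint, can be stopped without VRI being examined.

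*SAP*

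**What the plan says.** SAP 4.2.1 states: "The study has two primary efficacy endpoints: reduction in symptomatic COVID-19 disease and reduction in all VRI". Each has its own null hypothesis and its own share of the 0.05: 0.049 for COVID-19 and 0.001 for VRI. VRI includes COVID-19 (SAP 4.1). SAP 1.3 gives 87.1% power for COVID-19, and for the second endpoint says "The CMH chi-square test has 91% power to detect the difference between 10% and 2% rates of occurrence of VRIs".

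SAP 2.4 has two futility criteria.

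- **First review**, held "when 20% of the planned number of subjects have completed three weeks of treatment". If unblinding conditions are satisfied, "futility will be assessed using a conditional power approach assessing the efficacy of NTZ for the COVID-19 endpoint". The consequence is: "The IDMC will recommend stopping for futility if the conditional power of the study at that stage is less than 30" per cent.
- **Second review**, held "when 50% of the planned number of subjects have completed 6 weeks of treatment". Here "Futility will be concluded if the CMH test statistic for comparing the treatment groups on the COVID-19 endpoint is less than 0.179", which the SAP equates with a p-value above 0.3278.

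At both reviews the unblinded analysis depends on circumstances defined in the IDMC charter. These relate to the COVID-19 rate, to diarrhea and, at the second review, to other safety matters. The charter is not among the documents.

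The interim efficacy analysis in the same section does treat both endpoints, with 0.005 for COVID-19 and 0.0002 for VRI. VRI is left out of the futility rules only.

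**The concern.** With alpha split between two primary endpoints, the trial can succeed on either one. A futility rule for the whole study should therefore ask whether both are out of reach. The SAP's rules ask about one, and no text says the study would continue for the other.

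At the 50% review there is a further problem. When few COVID-19 cases have occurred, the CMH statistic is close to zero even if the drug works, so the rule can read shortage of cases as absence of effect. Low incidence is foreseeable: Protocol 8.1 says of SARS-CoV-2 that "infection control procedures may significantly decrease transmission". At stake is the chance to show benefit on VRI, the endpoint that matches the trial's broad-spectrum rationale.

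**Working it through.** **1. Reproduce the SAP's power.** Inputs from SAP 1.3: n = 400 per arm; 5% v 1% at alpha 0.047; 10% v 2% at alpha 0.001. With a continuity correction of 1/n = 0.0025,

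z = [|p1 − p2| − 1/n − z(1−α/2)·√(2p̄(1−p̄)/n)] / √([p1(1−p1) + p2(1−p2)]/n)

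- COVID-19: (0.0375 − 1.986 × 0.01206) / 0.01198 = 1.13, power 87.1% (SAP 87.1%).
- VRI: (0.0775 − 3.291 × 0.01679) / 0.01655 = 1.34, power 91.0% (SAP 91%).

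Both figures reproduce. They take no account of futility stopping.

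**2. Why few cases give a small statistic.** The corrected CMH statistic is (|Σ(a − E)| − 0.5)² / ΣV, with a the NTZ cases in a stratum, and E and V their null mean and variance. With equal arms, a stratum holding one case has E = 0.5 and V = 0.25. Suppose every case so far is on placebo, in different facilities:

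- 1 case: (0.5 − 0.5)² / 0.25 = 0
- 2 cases: (1 − 0.5)² / 0.5 = 0.5
- 3 cases: (1.5 − 0.5)² / 0.75 = 1.33

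So one case meets the rule however well the drug works.

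**3. Which bound.** The two printed forms of the 50% criterion disagree. A 1-df chi-square of 0.179 has an upper-tail p of 0.672; 0.3278 is its lower tail. A p-value of 0.3278 corresponds to a statistic of 0.958. This is a separate matter, so both versions are shown. By step 2, two cases split 2–0 meet the second version but not the first.

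**4. Expected cases at the 50% look.** With 200 per arm and an 80% reduction: 200 × 0.05 + 200 × 0.01 = 12 at the planned rate. By the same sum, 7.2, 4.8 and 2.4 cases are expected at placebo rates of 3%, 2% and 1%.

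**5. Effect on VRI power.** Simulation: 20 equal facilities, 400 subjects at the look and 800 at the end, NTZ cutting COVID-19 and other VRI by 80%. The continuity-corrected CMH is used throughout (the SAP specifies the correction for the final analysis and is silent for the interim). A VRI success is final p < 0.001 without having met the COVID-19 rule. Other VRI stays at the planned 10% − 5% = 5% on placebo. COVID-19 rates below 5% are assumptions.

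| Placebo COVID-19 | Rule met: 0.179 / p = 0.3278 | VRI power, no rule | With 0.179 | With p = 0.3278 |
|---|---|---|---|---|
| 5% (planned) | 4% / 12% | 94% | 91% | 84–85% |
| 3% | 15% / 31% | 82% | 73% | 61% |
| 2% | 25% / 49% | 72% | 58–59% | 42% |
| 1% | 50% / 77% | 58% | 33% | 17% |

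Repeat runs agree to about a point. The simulated 94% exceeds the SAP's 91% because step 1 is an approximation; compare along rows, not with the 91%.

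If other VRI falls in proportion to COVID-19, power with bound 0.179 goes from 58% to 54% at 3%, from 24% to 22% at 2%, and from 1.6% to 1.4% at 1%. With p = 0.3278 the loss is at most about 11 points.

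**6. First review.** On 80 per arm with half the 6-week rate, a working drug gives conditional power below 30% in 15% of trials at the 5% rate using the formula as printed. Reading sigma as a per-subject standard deviation gives 24%. At a 1% rate the share is 7–8%, and in about 61% of trials there are no cases and the formula is undefined. Fewer cases do not make this criterion easier to meet, so here the defect is only that VRI is not considered.

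**The case against.** Several stronger readings are tempting, and the documents do not support them.

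- **That low COVID-19 incidence by itself stops the trial.** Futility is assessed only if charter conditions open an unblinded analysis. Protocol 14 links possible additional futility analyses to more COVID-19 than expected, so a low count may not open that gate. A diarrhea or other safety trigger could open it at any COVID-19 rate, and Protocol 14 also plans a first interim analysis of safety and futility without that link. The risk remains, but the figures above are conditional on the rule being applied.
- **That both rules mistake few cases for no effect.** This is shown for the 50% rule only.
- **That meeting the rule necessarily ends the VRI test.** The first rule is an IDMC recommendation. The second says futility is concluded and names no action. What happens to VRI is unstated, which is itself the gap.
- **That the stated 91% VRI power is lost.** At the planned rates and bound 0.179, simulated power after the rule is still 91%.
- **That the loss at low rates is larger than tabulated.** Holding total VRI at 10% while COVID-19 falls to 1% would put other VRI at 9%, above the planned 5%. Protocol 8.1 expects infection control to reduce other respiratory viruses too. If they fall in step, the trial is unlikely to succeed on VRI anyway and the rule costs little.

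It can also be argued that COVID-19 is the lead endpoint: it carries 0.049 of the 0.05, and entry requires a recent case in the facility. A sponsor could choose to stop on it alone. But the plan does not state that choice, and it sits badly with a separately powered second primary endpoint that has its own interim efficacy alpha.

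**Conclusion.** The point holds as a gap in the futility rules. Both criteria ignore a primary endpoint, and nothing in the documents protects it. At the planned rates the cost is modest: about 3 points of VRI power with bound 0.179, and 9 to 10 with p = 0.3278. It becomes substantial, for example 72% to 58–59% or 42%, if placebo COVID-19 is about 2% while other viruses circulate as planned. It is at most about 4 points (bound 0.179) or 11 points (p = 0.3278) if all viruses fall together.

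These sizes assume that the charter conditions are met, that meeting the 50% rule stops the whole study, that NTZ is 80% effective against every virus, that strata are equal, and that a look with no COVID-19 cases counts as a statistic of zero. How often the charter would allow the analysis cannot be judged from the documents. The change is worth making before any unblinded review.

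**What to change.** In SAP 2.4 and the IDMC charter, do one of the following:

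- recommend stopping the study for futility only when both primary endpoints meet a futility criterion, with VRI judged at its own alpha (conditional power at the first review, a test-statistic bound at the 50% review); or
- state that COVID-19 futility drops only that endpoint and the study continues for VRI.

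If the 50% rule also required the VRI statistic to lie below the same bound, then with VRI at 10% v 2% and placebo COVID-19 between 0.25% and 5%, at most 0.8% of trials would meet it. At most 0.3% would be stopped trials that would have won on VRI. With placebo VRI at 6% (1% COVID-19, 5% other) the figures are 6.7% and 0.4%.

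The cost is wording and one more calculation per review. There is no type I error cost, because the final alphas take no credit for futility stopping (0.049 + 0.001 = 0.05 without an efficacy interim). The downside is that some trials with a futile COVID-19 hypothesis run on to the planned size for VRI, so the sponsor should make the choice explicitly.

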14. MONITORING THE STUDY

Monitoring will be conducted by the Sponsor and/or a contract research organization according to standard operating procedures. Site visits will be conducted by the Sponsor or their representatives at regular intervals to conduct inspections.

A full description of the monitoring procedures for this study will be detailed in the Clinical Monitoring Plan.

The Investigator will grant representatives of the Sponsor's clinical operations team and quality team, as well as regulatory agencies and ethical committees access to inspect facilities and records (including subject charts) relevant to this study and agrees to assist the monitors in their activities, if requested.

An Independent Data Monitoring Committee (IDMC) will be organized for this study. A full description of the IDMC procedures for this study will be detailed in the Medical Monitoring (Safety) Plan and IDMC Charter. The IDMC will closely monitor the incidence of diarrhea as it could potentially be a vehicle for the spread of SARS-CoV-2. Enrollment will be paused while the IDMC conducts its first interim analysis of safety and futility. The IDMC may also conduct analyses of safety, futility and effectiveness if the number of COVID-19 illnesses is higher than anticipated.

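### If the first futility look takes place and its rule is followed, an effective NTZ would meet the stopping rule in roughly 10% to 30% of trials, and the stated 87.1% power does not include this

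*SAP*

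**What the plan says.** SAP 2.4 sets a first IDMC review, described as one for safety, when 20% of the planned subjects have completed three weeks of treatment. An unblinded analysis may follow under IDMC charter conditions tied to the COVID-19 and diarrhea rates. If those conditions are met, futility on the COVID-19 endpoint is assessed by conditional power: "The IDMC will recommend stopping for futility if the conditional power of the study at that stage is less than 30" percent. The effect in the formula "is the observed study effect size (i.e., the difference in observed rates in the two groups"). Sigma is defined as the observed standard error of that difference, and the ratio is multiplied by the square root of n2, the number of subjects still to be enrolled. A second safety and futility review follows at 50%.

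Protocol 14 states no condition on futility: "Enrollment will be paused while the IDMC conducts its first interim analysis of safety and futility".

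SAP 1.3 says the CMH test "will have 87.1% statistical power to detect the difference between 5% and 1% rates" at a "two-sided alpha of 0.047 with a total sample size of 800". It does not mention a futility stop. SAP 2.4 expects 24 events in the whole study if the "COVID-19 rate is 0.05 in the placebo group and 0.01 in the NTZ group".

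**The concern.** Three weeks is half of the risk period and 160 subjects are a fifth of the sample, so the look may come at about a tenth of the planned information. Conditional power at the observed difference is then driven by one or two cases. A chance tie, or one extra NTZ case, reads as futility even when the drug works as the plan assumes. A stop of this kind leaves type I error alone but lowers power, and the stated power is the figure on which 800 subjects were judged enough. The formula as printed makes the rule cruder still.

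**Working it through.** **Inputs.** SAP 1.3 and 2.4: 400 per arm, 5% v 1% over six weeks, two-sided alpha 0.047. SAP 4.2.1: CMH test with continuity correction. SAP 2.4: first look at 20% × 800 = 160 subjects (80 per arm), stop below 30%. Assumptions: constant hazard, so three-week risks of 2.5% and 0.5%; n2 = 640.

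**1. The plan's own power.** Single-look two-proportion formula with correction 1/400:
- se0 = √(2 × 0.03 × 0.97/400) = 0.01206
- se1 = √((0.05 × 0.95 + 0.01 × 0.99)/400) = 0.01198
- power = Φ((0.04 − 0.0025 − 1.986 × 0.01206)/0.01198) = 87.1%

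This matches SAP 1.3 exactly, so no futility stop is in the figure. A simulated corrected CMH test over 20 LTCFs gives about 90%. That is the baseline for step 5.

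**2. Cases at the look.**
- 160 subjects at exactly three weeks: 80 × 0.025 + 80 × 0.005 = 2.4, or 2.4/24 = 10% of planned events.
- 160 subjects with six-week data: 80 × 0.05 + 80 × 0.01 = 4.8, or 20%.
- All enrolled subjects, assuming uniform accrual of 800 over 10 weeks: the look falls at week 5 with 400 enrolled and 2.5 weeks' mean follow-up, so 400 × 2.5/6 × 0.03 = 5.0. Accrual over 15 to 30 weeks gives 4.8.

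**3. The printed formula.** Take 1 placebo case v 0 NTZ cases:
- δ = 0.0125 and σ = √(0.0125 × 0.9875/80) = 0.01242, so δ/σ = 1.006. Multiplied by √640 = 25.3, this gives about 25.5.
- With two-sided p1 = 0.314, the square-root term is √(1.675² − 0.485²) = 1.60.
- Conditional power = 1 − Φ(1.60 − 25.5) ≈ 1.

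The excess 2 v 1, 3 v 2 and 4 v 3 also gives about 1. A deficit gives about 0. A non-zero tie gives 1 − Φ(1.675) = 4.7% with a one-sided p1 of 0.5, and is undefined with a two-sided p1 of 1. At 0–0, σ = 0 and the formula is undefined; that table has probability 0.975⁸⁰ × 0.995⁸⁰ = 8.8%. The rule therefore amounts to stopping unless placebo cases exceed NTZ cases.

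**4. Standard conditional power at the observed trend.** CP = 1 − Φ((1.986 − Z1/√t)/√(1 − t)). CP is below 30% when Z1 < √t × (1.986 − 0.524√(1 − t)), which is 0.471 at t = 0.1 and 0.679 at t = 0.2. Z1 is 1.00 for 1 v 0, 0.58 for 2 v 1 and 0.45 for 3 v 2. So 3 v 2 stops at t = 0.1, and 2 v 1 also stops at t = 0.2.

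**5. Probability that an effective NTZ meets the rule** (exact binomial, 80 per arm), and simulated power if the look always occurs and is obeyed (200,000 trials, alpha 0.047, no-stop power 90.1%):

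| Reading of the rule | 2.4 cases | 4.8 cases | Power, look at 2.4 cases |
|---|---|---|---|
| Printed, all ties stop | 24.0% | 9.4% | 70.4% |
| Printed, 0–0 does not stop | 15.1% | 8.6% | 78.0% |
| Current trend, t = 0.1 | 25.0% | 13.1% | 69.5% |
| Current trend, t = 0.2 | 32.4% | 18.4% | 63.1% |

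The matching t is 0.1 for 2.4 cases and 0.2 for 4.8. Using all enrolled subjects gives 9–10% (printed, all ties stop) and 18–19% (current trend). If no tie counted as a stop, the printed rule would leave 6.2% at 2.4 cases, but a rule that passes a zero difference is hardly intended.

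**The case against.** The strongest objection is that the look is conditional. SAP 2.4 assesses futility only after charter conditions are met, the IDMC only recommends, and the trigger depends partly on the same case count that drives a false stop. A reader might infer that the plan will stop an effective drug one time in four, or that the trial's true power is 70%. The documents do not support either statement: the probability that the look occurs is unknown, and 2.4 cases is a floor.

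The condition does not remove the problem, though. Using the current-trend rule at t = 0.1 and 2.4 expected cases, the false-stop probability given the look is 11% if unblinding needs at least three cases (4.6% counted over all trials), 14% if it needs at least four (3.1%), and about 36% if a low count of at most two triggers it. These triggers are illustrations only. A diarrhea trigger would add no COVID-19 information.

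It is also fair that conditional power at the observed trend is a recognised choice, that type I error is not inflated, and that the 50% look is a separate safeguard against continuing with an ineffective drug. These points lower the severity. They do not put the stop into the 87.1%.

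**Conclusion.** The point holds in conditional form, as a should-fix. If the first unblinded look takes place and its rule is followed, an effective NTZ meets the rule in roughly 10% to 30% of trials: about 24–25% at 2.4 expected cases and about 9–19% at about 5. If the look always occurs on three-week data and is obeyed, simulated power falls from about 90% to about 70% (63–78% across readings). The unconditional loss cannot be computed from the documents.

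Two findings do not depend on the trigger. The 87.1% is a single-look figure with no futility stop in it. The printed formula puts sigma and n2 on mismatched scales and fails at 0–0.

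The sizes rest on the planned 5% v 1% rates, constant hazard, and 80 per arm at the look or, where stated, uniform accrual.

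**What to change.** 1. In SAP 1.3, restate the power with the futility rules in force, given that the looks occur, beside the single-look figure.
2. In SAP 2.4, correct the conditional-power formula so that sigma and n2 are on matching scales. State whether p1 is one- or two-sided, how ties and 0–0 tables are handled, which subjects' data are used, and any minimum case count. State or summarise the charter trigger.
3. Either make no futility decision at the first look and leave it to the existing 50% look, or compute first-look conditional power at the design effect and keep the 30% limit. The second option has a plain consequence. With drift 3.1 and t = 0.1, a stop needs Z1 below (1.969 − 3.1 × 0.9 − 0.524 × √0.9)/√0.1 ≈ −4.2. With three-week data this in effect switches off first-look futility.
4. Reconcile Protocol 14, which calls the first interim one of safety and futility, with the conditional wording of SAP 2.4.

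The changes are to wording only. The price is that an ineffective NTZ (5% v 5%) is no longer caught early. Under the design-effect option it is stopped at the first look about 0% of the time with three-week data, or about 1% with six-week data, against 67–74% under the current-trend rule. That task passes to the 50% look.
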